#### **12.3 Statistical analysis:**

All primary analyses will be performed using intent-to-treat principles. Baseline characteristics will be compared using descriptive statistics (e.g., frequency tables and percentages for categorical variables; means, medians, standard deviations, ranges for continuous variables), and p-values will be calculated using appropriate statistical tests (e.g., chi-square, t-test, Mann-Whitney). Our primary analytic approach will be mixed effects linear regression which will enable efficient estimation of intervention effects and inclusion of all subjects in intent-to-treat analyses. Analyses will focus on differences in outcomes between the groups over time. Fixed effects terms will be included for group (immediate vs. delayed start), time (0, 3, 6 or 9 months), and the interaction between group and time, with time modeled as a dummy variable. Subjects and cohorts will be modeled as random effects. Models also will adjust for any baseline differences between groups that may occur by chance. Covariates will be included to adjust for any co-interventions that may occur (e.g., medication changes). Sensitivity analyses will be performed to determine the effects of compliance on intervention effects. Graphs and diagnostic tests will be used to assess for outliers and influence points. Line plots will be used to visually examine change over time by group.

Sub-Study: We will conduct qualitative analyses of the transcribed audio recordings from 10 interviews..

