### 14.4 Explain how and why the number of subjects was chosen (Help Text updated 9/13):

Sample size estimates and power calculations are based on a repeated measures design with 1 pre and 3 post measures using between-group effect size estimates from our pilot study, correlation between measures of 0.75 (based on our pilot data) and alpha=0.05. Sample size estimates at 80% power ranged from n=8/group to n=22/group depending on the effect size. Conversely, power estimates using a sample size of 30/group ranged from 91% to 100%. Power will be >80% for all outcomes even with 20% attrition. We also estimate that 60% of those screened will be eligible and agree to participate based on our previous studies. There we anticipate screening a total of 100 dyads in order to reach our target sample size of 60 dyads.

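### The primary model fits a separate month-0 mean for each randomised group, so its month-3 contrast is an unbiased change-score comparison that is about 11–12.5% less efficient than one using the baseline already collected

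*Combined protocol and SAP*

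**What the plan says.** Section 12.3 makes mixed-effects linear regression the primary analysis. On the fixed effects it says "Fixed effects terms will be included for group (immediate vs. delayed start), time (0, 3, 6 or 9 months), and the interaction" and continues "between group and time, with time modeled as a dummy variable". On the random part it says "Subjects and cohorts will be modeled as random effects". The tested contrast is described only as group differences over time; no visit is named.

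Two sentences in 12.3 concern baseline. For the comparison of baseline characteristics, "p-values will be calculated using appropriate statistical tests". For the outcome models, "Models also will adjust for any baseline differences between groups that may occur by chance". No covariate is listed, no threshold is given, and the outcome's own baseline value is not named as a covariate. Covariates for co-interventions are planned separately.

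Section 14.4 sizes the trial on a "repeated measures design with 1 pre and 3 post measures", with "correlation between measures of 0.75 (based on our pilot data) and alpha=0.05". Under 11.1 the delayed-start group receives the program after month 3.

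**The concern.** A group main effect, time dummies that include month 0, and their interaction together give each group a free mean at every visit. The month-3 interaction then subtracts the observed baseline difference in full. Under randomisation the expected baseline means are equal, so the observed difference is noise. Subtracting all of it is too much whenever the correlation between baseline and follow-up is below 1.

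Two things are at stake. The first is precision at month 3, where caregiver burden has the smallest of the pilot effects given in 13.2. The second is pre-specification: a rule that adjusts for whatever differences turn up chooses covariates after the data are seen, and the reported effect can vary with that choice.

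**Working it through.** **Inputs.** Correlation r = 0.75, alpha 0.05, 30 per group and 20% attrition (24 per group) come from 14.4. Standardised effects d of 0.83, 0.76 and 0.49 come from 13.2. Assumptions: alpha is two-sided, d is on the raw outcome SD scale, the correlation is equal across visits, and cohort effects cancel within cohorts.

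**Variance factors.** The variance of the group contrast is 2k/n per unit SD². With p post measures and one pre measure:
- change score: k = (1+(p−1)r)/p + 1 − 2r
- baseline-adjusted: k = (1+(p−1)r)/p − r²

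**Reproducing 14.4 (p = 3).** Change score: k = 0.8333 + 1 − 1.5 = 0.3333. Then n = 2(1.960+0.842)²k/d² gives 7.6, 9.1 and 21.8, which round up to 8, 10 and 22 per group. Power at 30 per group runs from 90.8% to 99.98%. At 24 per group it is 83.6% for d = 0.49. These match the stated 8 to 22, 91% to 100%, and above 80% with attrition. The baseline-adjusted formula gives 7 to 18, and a post-only analysis gives 19 to 55. The sizing therefore assumes a change-score analysis.

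**Month-3 contrast (p = 1).**
- Change score: k = 2(1−0.75) = 0.50; variance 2×0.50/30 = 0.03333.
- Baseline-adjusted: k = 1−0.75² = 0.4375; variance 2×0.4375/30 = 0.02917.
- Saving: 1 − 0.4375/0.50 = 12.5%; in general (1−r)/2.

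Generalised least squares for four visits with compound symmetry and 30 per group gives the same two variances for the planned model and for the model with a common month-0 mean.

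**Finite sample.** Estimating the baseline slope inflates the adjusted variance by about 1 + 1/(N−4). At N = 60 that is 1.018, and the saving becomes 1 − 0.4375×1.018/0.50 = 10.9%. A simulation at this size gave 10.5%.

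**Other values.** The single-visit saving is 25% at r = 0.50 and 7.5% at r = 0.85. For the 1-pre/3-post average of 14.4, k falls from 0.3333 to 0.2708, a saving of 18.75%. With two post visits (11.1 lists only months 3 and 6), it is 16.7%.

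**Month-3 power, d = 0.49.**

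| n per group | Method | As planned | Baseline-adjusted |
|---|---|---|---|
| 30 | normal | 76.5% | 81.8% |
| 30 | t, slope estimated | 75.1% | 79.8% |
| 24 | normal | 67.0% | 72.8% |
| 24 | t, slope estimated | 65.2% | 70.0% |

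**Does the chance-imbalance sentence recover the loss?** Not if the covariate enters as a main effect. A baseline covariate is constant within a subject, so it cancels from the within-subject contrast when data are complete. In 300 simulated complete datasets, adding one changed the month-3 interaction estimate by at most 9e-16.

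**The case against.** The planned model is a standard longitudinal analysis and is unbiased under randomisation. The sizing in 14.4 already allows for it: on the plan's own 1-pre/3-post basis, power for d = 0.49 is 90.8% at 30 per group and 83.6% at 24. Power below 80% appears only when month 3 is isolated, and the plan does not name that contrast. The shortfall there comes from the delayed-start design, not from the handling of baseline. All of this stands, and it makes the point one of efficiency rather than error.

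A reader might infer that baseline p-values decide which covariates enter. Section 12.3 does not say so: the p-values and the adjustment rule appear in separate sentences with no link and no threshold. What can be said is that the rule is undefined and depends on observed differences.

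A reader might also infer that the change lifts caregiver burden above 80% power at month 3. That holds under the normal approximation (81.8%) but not with t-based power and an estimated slope (79.8%), and not at 24 per group by either method.

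Finally, a common month-0 mean is assured only if baseline is measured before allocation is known. Section 16.1 lists randomisation before assessments but gives no order between allocation and the baseline visit, and caregiver questionnaires can be self-administered. This condition is a real limit on the fix.

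**Conclusion.** The point holds as a modest, nearly costless gain in precision together with a gap in pre-specification. For the month-3 contrast the saving is 12.5% of the variance in large samples and about 10.5–11% at 60 dyads. By 1/(1−0.109) = 1.12, the latter is worth about 12% more dyads. For the three-visit average of 14.4 the large-sample saving is about 19%.

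The figures rest on r = 0.75, complete data, equal correlation across visits, pilot effects on the raw SD scale, and the group-by-time term being the one tested. The documents do not support a reading of bias or of an error in the sample size: 14.4 is consistent with the change-score analysis that 12.3 describes.

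**What to change.** In 12.3:

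1. Drop the group main effect so that the month-0 means are constrained equal. Keep the time terms and the group-by-time terms for post-baseline visits. Baseline stays in the outcome vector, so all randomised dyads with a baseline remain in the model.
2. State that baseline is assessed before allocation is known. If that cannot be guaranteed, model the post-baseline visits with the baseline outcome as a covariate instead. Use one approach or the other, since the same measurement should not be both a constrained outcome and a covariate. The two are not identical when follow-up is missing: the covariate version drops dyads with no follow-up, which sits less well with the plan's aim of including everyone.
3. Replace the adjustment for chance baseline differences with a short list fixed in advance, for example baseline CDR, which is obtained at screening. Cohort is already a random effect and should stay one. Say that baseline p-values play no part in choosing covariates.
4. Name the contrast to be tested, including the month-3 comparison.

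The cost is wording only, with no new data. The small downside is that the constraint relies on baseline being measured before allocation is known.

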### 13.2 Preliminary studies:

Our group has recently pioneered a novel, multi-domain program called Preventing Loss of Independence through Exercise (PLIÉ, pronounced 'plee-ay'). PLIÉ integrates physical activity (training of procedural memory for basic daily activities such as transitioning safely between sitting and standing), cognitive stimulation (mindful body awareness), social engagement (group movement and sharing of in-the-moment experiences), music, and caregiver education (monthly home-visit). We studied PLIÉ in individuals with mild to moderate dementia who were attending an adult day program in San Francisco, CA, and found evidence that those who participated in PLIÉ for 45 minutes, 2-3 days per week for 4 months (total: 26-39 hours) experienced improvements in a wide range of outcomes compared to a Usual Care (UC) control group that participated in standard chair-based exercises. Standardized, between-group effect sizes were moderate to large on validated measures of quality of life (0.83), cognitive function (0.76) and caregiver burden (0.49).

Although PLIÉ was originally designed and tested in an adult day care setting, most people in the community do not have access to a day care center, are concerned about the stigma associated with day care or are unable to afford it. **There is a huge need for innovative, rigorously-tested programs that can be performed together by affected individuals and their care partners, either in group settings or at home.** The Paired PLIÉ Program was specifically designed to address this critical need in the community. Over the past year, we have systematically created the Paired PLIÉ program by adapting the original PLIÉ protocol to be performed by dyads of affected individuals and care partners.

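### Section 12.3 leaves the within-subject covariance unspecified; on its plain reading it assumes equal correlation across visits, which mis-scales the month-3 and month-9 standard errors if correlation falls with lag

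*Combined protocol and SAP*

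**What the plan says.** Section 12.3 makes mixed effects linear regression the primary analysis. Its fixed effects are group, "time (0, 3, 6 or 9 months), and the interaction between group and time, with time modeled as a dummy variable". It then says "Subjects and cohorts will be modeled as random effects". It does not say whether the subject effect is an intercept only, what covariance the residuals have, or whether standard errors are model-based or robust. No visit or contrast is named as primary; the stated focus is general: "Analyses will focus on differences in outcomes between the groups over time".

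Section 14.4 bases power on a "repeated measures design with 1 pre and 3 post measures using between-group effect size estimates from our pilot study", with "correlation between measures of 0.75 (based on our pilot data) and alpha=0.05". One correlation therefore serves for visits 3, 6 and 9 months apart. Section 13.2 describes a pilot with a 4-month intervention and gives effect sizes of 0.83 (quality of life), 0.76 (cognition) and 0.49 (caregiver burden).

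The outcome schedule differs between sections. Section 12.3 and section 16.1 (item 5, Assessments) run to 9 months, while section 11.1 collects outcomes to 6 months. Section 11.1 also has Group 1 move to maintenance, and Group 2 start classes, after month 3.

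**The concern.** A subject random intercept with independent residuals gives all visits one variance and all pairs of visits one correlation. A single pooled residual variance then sets the standard error of every group-by-time contrast. The 0.75 comes from a pilot with a 4-month intervention but is applied to visits up to 9 months apart, in a progressive condition, with the two groups changing activity at month 3. Correlation may well be lower at longer lags.

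If so, two things go wrong. Month 3 is the only post-baseline visit that compares treated with not-yet-treated pairs, so it bears most directly on Hypotheses 1 and 2; its standard error would be inflated by the noisier later changes. Later contrasts, which feed the aims framed over 9 months, would be tested with standard errors that are too small.

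**Working it through.** **Inputs.** From the plan: 30 per group (60 dyads, 1:1), correlation 0.75, alpha 0.05 (taken as two-sided), effects 0.49, 0.76 and 0.83, visits at 0, 3, 6 and 9 months. Assumed here: unit variance at every visit, 0.75 as the correlation at the 3-month lag, and the decline at longer lags.

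**The plan's own figures.** For the mean of three post visits minus baseline under equal correlation, V = (1 + 2×0.75)/3 + 1 − 2×0.75 = 0.3333. Then n per group = 2(1.96 + 0.842)²V/d² = 5.23/d²: 8 for 0.83, 10 for 0.76 and 22 for 0.49. Power at 30 per group is 90.8% to 99.98%, and for 0.49 at 24 per group about 84%. This matches the 8 to 22 per group, the 91% to 100%, and the claim of more than 80% after 20% attrition. The power calculation thus rests on equal correlation too.

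**Standard-error ratio.** With complete balanced data, the random-intercept model gives each change from baseline a variance proportional to 1 − mean(ρ), averaged over the six visit pairs (three at 3 months, two at 6, one at 9). The true variance is proportional to 1 − ρ(visit). Hence model SE / true SE = √[(1 − mean ρ)/(1 − ρ(visit))].

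Example, 0.75/0.70/0.65: mean ρ = (3×0.75 + 2×0.70 + 0.65)/6 = 0.717. Month 3: √(0.2833/0.25) = 1.065. Month 9: √(0.2833/0.35) = 0.900. The month-9 false-positive rate is 2[1 − Φ(1.96×0.900)] = 7.8%.

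For mean post minus baseline, the model variance is (4/3)(1 − mean ρ) and the true variance is (3 + 4ρ₃ + 2ρ₆)/9 + 1 − 2(ρ₃ + ρ₆ + ρ₉)/3. In the same example: √(0.3778/0.4222) = 0.946, or 6.4%.

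| Correlation at 3/6/9-month lag | Mean ρ | SE ratio, month 3 | SE ratio, month 9 | False positives, month 9 | False positives, mean post − baseline |
|---|---|---|---|---|---|
| 0.75 throughout | 0.750 | 1.00 | 1.00 | 5.0% | 5.0% |
| 0.75/0.70/0.65 | 0.717 | 1.065 | 0.900 | 7.8% | 6.4% |
| 0.75/0.65/0.55 | 0.683 | 1.125 | 0.839 | 10.0% | 7.5% |
| Autoregressive 0.75/0.56/0.42 | 0.633 | 1.212 | 0.797 | 11.8% | 8.5% |

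**Month-3 power, 30 per group.** True SE = √(2×2×(1 − 0.75)/30) = 0.1826, and power = Φ(d/0.1826 − 1.96×ratio).

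| Effect | Correct SE | 0.75/0.70/0.65 | 0.75/0.65/0.55 | Autoregressive |
|---|---|---|---|---|
| 0.49 | 76.5% | 72.5% | 68.4% | 62.1% |
| 0.76 | 98.6% | 98.1% | 97.5% | 96.3% |
| 0.83 | 99.5% | 99.3% | 99.0% | 98.5% |

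At 24 per group, power for 0.49 falls from 67.0% to 62.3%, 57.7% and 51.0%.

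**If month 6 is the last visit.** With 0.75/0.70 the month-6 ratio is √(0.2667/0.30) = 0.943, or 6.5% false positives. With the autoregressive pattern it is √(0.3125/0.4375) = 0.845, or 9.8%.

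**Simulation checks.** In 40,000 trials per scenario, month-3 power for 0.49 went from 75.6% to 72.8% (mild decline) and from 74.8% to 61.9% (autoregressive). Visit-specific variances gave 4.9-5.1% false positives at every visit. Mixed models fitted to autoregressive data with about 20% dropout gave 10.3% at month 9 with a random intercept (600 trials) and 6.7% with a random slope added (300 trials).

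**The case against.** A reader might infer that the plan commits to equal correlation, that its 9-month tests would run at up to 12% false positives, and that month-3 power would drop by up to 14 points across the outcomes. The documents do not support that.

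- **Model form.** Section 12.3 never says intercept only, independent residuals or model-based standard errors. A random slope would fit its wording and would remove most of the month-9 error: the 6.7% above has a Monte Carlo standard error of about 1.4 points and cannot be told apart from 5%.
- **Decline.** No section says that correlation falls with lag, or over what interval the 0.75 was measured; section 13.2 gives only the length of the intervention. On the plan's single 0.75 the error rate is 5% at every visit. The autoregressive case, with 0.42 at 9 months, is an extreme that leaves no lasting difference between people.
- **Effect size.** The large power loss belongs to 0.49 alone.
- **Contrast.** Month 9 is not a named test. Aims over 9 months describe a period, both groups have been offered the program by then, and section 11.1 stops outcomes at month 6. The contrast that reproduces section 14.4 is less affected.

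All of this stands as a limit on size. It does not remove the point, because nothing in the plan protects against a decline, and intercept only is the ordinary reading of a subject random effect with nothing further specified.

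**Conclusion.** The point holds as an unspecified covariance whose default reading gives valid standard errors only if variance and correlation are the same across visits. It is not an error on the plan's own figures.

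If correlation is 0.75 at 3 months and declines over the range examined, the month-3 test is conservative (standard error 6-21% too large) and the month-9 test is anticonservative (10-20% too small, about 8-12% false positives). The mean-post contrast runs at about 6-9%, and a final month-6 visit at about 6.5-10%. The month-3 cost in power is material for caregiver burden, a named Hypothesis 2 outcome with pilot effect 0.49 (about 3-14 points at 30 per group), and slight for the two larger effects (about 0-2 points).

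These sizes assume intercept-only random effects, equal variances, 0.75 at the 3-month lag and, apart from the dropout check, complete data. The change is cheap and should be made before analysis.

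**What to change.** In section 12.3, keep the fixed effects and the cohort random effect. Replace the subject random intercept with an unstructured within-subject covariance over the scheduled visits, fitted by REML with Kenward-Roger degrees of freedom. Four visits need 4 variances and 6 covariances, 10 parameters in all, which is routine with about 60 subjects.

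Prespecify the fallback if the model does not converge: heterogeneous Toeplitz, then a random intercept with standard errors robust at the subject level. The level should be stated, because enrolment in blocks of 10 gives only 60/10 = 6 cohorts, too few to cluster on.

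Reconcile the outcome schedule in section 11.1 (to 6 months) with sections 12.3 and 16.1 (to 9 months), so that the covariance covers the visits actually made.

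The cost is wording, about 1 point of power if correlations are truly equal, and a possible convergence fallback. The 1-point figure was obtained for complete balanced data; it was not checked with the cohort term and attrition together.

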## 11.0 Study Design

### 11.1 \* Study design (Help Text updated 9/13):

We propose to perform a randomized, controlled trial (RCT) with a delayed start design to examine the effects of the Paired PLIÉ program in individuals with cognitive impairment and their care partners over 9 months. Study participants will be 60 pairs of individuals with mild-to-moderate cognitive impairment and their primary care partners. Study pairs will be enrolled in blocks of 10 and will be randomly assigned to Group 1 (immediate start, n=5) or Group 2 (3-month delayed start, n=5). Pairs randomized to Group 1 will participate together in the Paired PLIÉ program 2 days/week for 12 weeks (24 classes total) while pairs randomized to Group 2 will continue with their usual activities. After 3 months, Group 1 will transition into a maintenance phase, and Group 2 will participate in the Paired PLIÉ program 2 days/week for 12 weeks. Outcome data will be collected in all study participants at baseline and 3, and 6 months. We have partnered with local community-based organizations that have agreed to serve as study sites and to assist with recruitment efforts.

We will conduct a sub-study with semi-structured interviews in a sub-sample of our participants. The goal is to assess motivations and barriers for home practice of the exercises taught in the intervention classes and to develop improved support materials (brochures, video clips on DVD and/or YouTube) according to feedback from participants.

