#### 14.7 Exclusion criteria:

*Affected Individuals:* behavioral or physical issues that would be disruptive or dangerous to themselves or others (e.g., active psychosis, drug abuse, severe behavioral issues); planning to move to a facility before the end of the study period; terminal illness (life expectancy < 1 year); non-stable dementia medication dose; current participation in another research study; unwilling to be video-recorded for quality control purposes.

*Caregiver/care partner:* planning to place affected individual in an institutional setting during the study period; terminal illness (life expectancy < 1 year); behavioral or physical issues that are disruptive or dangerous; unwilling to be video-recorded for quality control purposes.

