**6. Qualitative data.** Exercise instructors or other research staff may record qualitative observations of participants and/or caregivers including changes in movement abilities, emotional state, or cognitive function of participants within the class setting over time, and in response to specific exercise interventions as they are introduced. Comments made by participants and caregivers related to the exercise class may also be recorded. Semi-structured interviews also may be conducted with caregivers to assess feasibility and acceptability of the program, barriers to home practice and suggestions for improvements.

**7. Compliance, co-interventions and adverse events.** Compliance will be assessed based on class attendance. In addition, caregivers will be asked to complete weekly reflection journals. Monthly check-in calls will be performed with caregivers to assess for adverse events, falls and co-interventions (e.g., changes to medications or daily routine) and to address issues related to non-compliance and barriers to practice. If caregivers request, monthly check-ins may be conducted via mail, email, fax or text. Caregivers will be informed that these modes of communication may increase their risk of loss of privacy. Mail, email, fax and text communications will include a confidentiality statement. The minimum amount of identifying information will be included in all communications. Study forms will include unique study ID numbers only.

**8. Video-Recording.** Some exercise classes and assessments may be video-recorded for quality control and educational purposes. Study participants will be able to consent to video recording for research and educational purposes (private viewing only) or public release of video recordings (public + private viewing). If any person who has not consented enters the video frame, this section will be deleted. Other persons may be staff at the study sites. Video recordings will be saved in a MyResearch folder only in the edited version (without any non-consented person in the frames). All other video recordings will be deleted from the camera after downloading on a secured server or an encrypted external hard drive stored in a secure locked file cabinet and will not be stored on any computers.

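### Section 12.3 adjusts the primary model for co-interventions recorded after randomisation, without stating the coding or planning an estimate free of that adjustment

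*Combined protocol and SAP*

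**What the plan says.** Section 12.3 opens with the principle "All primary analyses will be performed using intent-to-treat principles" and names mixed effects linear regression as the primary approach. It lists the fixed effects (group, time as dummies at 0, 3, 6 and 9 months, and their interaction) and the random effects (subjects and cohorts), then adds adjustment for chance baseline differences. The next sentence is "Covariates will be included to adjust for any co-interventions that may occur (e.g., medication changes". Only after that do sensitivity analyses appear, and they concern compliance: "Sensitivity analyses will be performed to determine the effects of compliance on intervention effects". The section also plans line plots of change by group, which are descriptive and give no effect estimate.

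Section 16.1, item 7, has monthly check-in calls that ask about "co-interventions (e.g., changes to medications or daily routine". Section 16.6 budgets nine such calls for caregivers. Section 14.7 excludes "non-stable dementia medication dose" at entry. Under section 11.1, Group 1 attends classes twice a week for 12 weeks, "while pairs randomized to Group 2 will continue with their usual activities".

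**The concern.** A co-intervention noted at a monthly call is a post-randomisation variable. Assignment can influence it in two ways. The programme may change what people do or take. It may also change how they fare, and their course may then prompt a medication change. Holding such a variable fixed answers a different question from the one section 12.3 sets.

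Everyone is still analysed in the arm to which they were randomised, so the issue is which effect is estimated, not who is included. The group-by-time contrast is the trial's headline result. As the plan stands, it could depend on a coding choice left open until the data are in hand, with no unadjusted result planned beside it.

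**Working it through.** **1. The plan's own figures.** Inputs are the pilot effects in section 13.2 (0.83 for quality of life, then "cognitive function (0.76) and caregiver burden (0.49"), and from section 14.4 one pre and three post measures, alpha 0.05 and "correlation between measures of 0.75 (based on our pilot data". Two-sided testing is assumed because it reproduces the figures. The variance factor for the mean of three post measures minus baseline is (1 + 2×0.75)/3 + 1 − 2×0.75 = 0.333.

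- n per group at 80% power = 2 × (1.960 + 0.842)² × 0.333 / d². This gives 7.6, rounded up to 8, for d = 0.83; 9.1, rounded up to 10, for d = 0.76; and 21.8, rounded up to 22, for d = 0.49.
- Power for d = 0.49 at 30 per group: SE = √(2 × 0.333/30) = 0.149, so Φ(0.49/0.149 − 1.96) = 90.8%.
- At 24 per group (20% attrition): SE = 0.167 and power is 83.7%.

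These match the stated 8 to 22 per group, 91% to 100%, and above 80%. The calculation contains no covariates, so this point does not touch it.

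**2. Where the adjustment sits.** In section 12.3 the order is: primary model, fixed effects, random effects, baseline adjustment, co-intervention covariates, then sensitivity analyses for compliance. Nothing assigns the co-intervention covariates to a secondary model. This is an inference from position, since the sentence does not itself name a model.

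**3. Route A: use differs by arm and the co-intervention affects the outcome.** Let τ be the total effect of assignment, γ the co-intervention's effect, and Δp the arm difference in use (immediate minus delayed). With time-varying or covariate-by-time coding, and use unrelated to the person's course, the contrast estimates τ − γΔp. The documents give neither γ nor Δp. Assumed ranges are 10 to 30 points for Δp, in either direction, and 0.2 to 0.5 SD for γ:

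- smallest shift: 0.10 × 0.2 = 0.02 SD
- largest shift: 0.30 × 0.5 = 0.15 SD

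A true 0.49 would be estimated at 0.47 to 0.34 if a helpful co-intervention is commoner in the immediate arm, or at 0.51 to 0.64 if it is commoner in the delayed arm. For scale, the SE of the month-3 contrast at 30 per arm is √(2 × 2(1 − 0.75)/30) = 0.183, so 0.15 SD is about 0.8 of a standard error.

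**4. How far the coding matters.** This is a large-sample simulation with four visits, compound symmetry 0.75, a true total effect of 0.49, use of 40% against 10%, γ = 0.5 and 20% random dropout by month 9:

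| Coding of the co-intervention | Estimate |
|---|---|
| Not in the model | 0.492 |
| Subject-level main effect | 0.492 |
| Time-varying | 0.341 |
| Covariate-by-time | 0.339 |

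A subject-level main effect moves a person's level at all visits alike, so it leaves the group-by-time contrast alone. At trial size (30 per arm) with time-varying coding, reversing use to 10% against 40% gave 0.637. Equal use (20% in each arm) gave no shift.

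**5. Route B: a poorer course prompts the change.** Here the medication change has no effect of its own. Its probability depends on the interim course, logit = −1.4 − b × course in SD units, which is about 20% at a course of zero. With a true effect of 0.49, 30 per group, and the covariate in a regression of the change score:

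| b | Unadjusted | Adjusted |
|---|---|---|
| 0 | 0.49 | 0.49 |
| 1 | 0.49 | 0.47 |
| 2 | 0.49 | 0.42 |
| 3 | 0.49 | 0.38 |

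Two further runs of the same mechanism gave 0.47, 0.44, 0.39 and 0.44, 0.37, 0.33. The overall range is roughly 0.33 to 0.47. Route A's formula would predict no shift here because γ = 0, so it is not a full account of what can go wrong.

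**The case against.** The strongest reply is that the defect is conditional. A subject-level main effect produces no shift, and the sentence directly follows a subject-level adjustment for baseline differences, so that coding is a natural reading. Placement in the primary model is itself inferred. Both points stand. They show that the plan leaves the matter open, not that it is safe.

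Second, the upper end of the assumed range fits the documents poorly. The only example in section 12.3 is medication changes. Section 13.1 describes the effects of dementia drugs as relatively small, and section 14.7 excludes unstable dementia medication at entry. This also stands. At 0.2 SD, route A gives only 0.02 to 0.06 SD (0.10 × 0.2 to 0.30 × 0.2), so 0.15 SD is a worst case. The exclusion does not prevent later changes, however, and does not cover other medications or daily routine. Route B needs no drug effect at all.

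Third, a reader might infer that class attendance would itself be coded as a change in daily routine and adjusted away. The documents do not support that. A co-intervention ordinarily means something other than the study programme, and section 16.1 is silent on routine changes made in order to attend.

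Fourth, stating the coding and reporting both estimates might be thought enough. That would close most of the gap, but it leaves open which estimate is the headline. The intent-to-treat commitment in section 12.3 points to the unadjusted one.

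**Conclusion.** The point holds as a cheap improvement to a stated rule. As written, section 12.3 places post-randomisation covariates in the model meant to deliver the intent-to-treat effect, does not say how they are coded, and plans no estimate without them. With time-varying or covariate-by-time coding, and use that differs by arm or follows the outcome's course, the group-by-time contrast departs from the total effect of assignment. If use is unrelated to both, or a subject-level main effect is used, it does not.

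Size and direction cannot be derived from the documents. The 0.02 to 0.15 SD shift in either direction, and the fall from 0.49 to roughly 0.33 to 0.47, rest wholly on assumed inputs.

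Three stronger readings are not supported:

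- **A general inflation of the false-positive rate.** Under route A, a zero total effect with a non-zero shift requires a direct programme effect that exactly cancels the effect carried by the co-intervention. Carrying one shift through months 3, 6 and 9 would further ignore the delayed arm starting the programme after month 3. Cancellation is not the only possible route: with no programme or co-intervention effect, but use that differs by arm and is tied to a poor course, one run gave about 9% rejection. That too depends on inputs absent from the documents, so no error rate can be attached to this trial.
- **A faulty sample size.** The figures in section 14.4 reproduce and are unaffected.
- **A breach of analysis as randomised.** No one is excluded or moved between arms.

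**What to change.** In section 12.3:

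- Make the mixed model without post-randomisation co-intervention covariates the primary analysis.
- Tabulate co-interventions by arm and visit.
- Keep the co-intervention-adjusted model as a labelled sensitivity analysis. State its coding (time-varying, subject-level or covariate-by-time) and whether routine changes made to attend the programme count.

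This takes two or three sentences and no new data, since the monthly calls already collect what is needed. The downside is that a co-intervention imbalance arising by chance is no longer adjusted for in the headline estimate, though it remains visible in the table and the sensitivity analysis.
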